6.1.1. Analysis Population

The following major analysis populations will be used (additional analysis populations for specific analysis will be defined in the corresponding analysis section):

Intent-to-Treat Population (ITT): Unless otherwise specified, efficacy and health outcomes analyses for Period 2 (Induction Dosing Period) will be conducted on the intent-to-treat (ITT) population, defined as all randomized patients, even if the patient does not take the assigned treatment, does not receive the correct treatment, or otherwise does not follow the protocol. Patients will be analyzed according to the treatment to which they are assigned.

Per Protocol Set (PPS): In addition, the primary analysis will be repeated using the per protocol set (PPS), which is defined as all randomized patients who are compliant with therapy, who do not have a subset of important protocol deviations that impact the primary efficacy endpoint (Section 6.5), and whose investigator site does not have significant good clinical practice (GCP) issues that require a report to the regulatory agencies prior to Week 12 (Visit 7). Compliance with therapy is defined to be missing no more than 20% of expected doses, not missing 2 consecutive doses, and no double dosing (that is, taking more injections at the same time point than specified in the protocol) during the period that patients participated in the study and prior to Week 12 (Visit 7) (see Section 6.8). Patients will be analyzed according to the treatment to which they are assigned.

Safety Population: Safety analyses for Period 2 will be conducted on the Safety Population, defined as all randomized patients who received at least 1 dose of study treatment. Patients will be analyzed according to the treatment to which they were assigned.

Maintenance Dosing Period Primary population: defined as all re-randomized patients (that is, patients randomized to ixekizumab in Period 2 who achieved an sPGA (0, 1) and were re-randomized at Week 12) who received at least 1 dose of study treatment during Period 3.

Patients will be analyzed according to the treatment to which they were re-randomized. Only information prior to relapse will be presented.

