Maintenance Dosing Period Secondary population: defined as the ixekizumab patients who were not re-randomized at Week 12 or patients who were randomized to placebo at Week 0, who received at least 1 dose of study treatment during Period 3. Patients will be analyzed according to the treatment to which they were assigned upon entry into Period 3.

Maintenance Dosing Period Relapse population: defined as all patients who were responders at Week 12 (that is, patients who achieved an sPGA (0,1) at Week 12) who first experience a relapse (sPGA ≥ 3) at any point during the maintenance dosing period (that is, Period 3). Although all patients will receive 80 mg Q4W, patients will be analyzed according to the treatment to which they were re-randomized or assigned at Week 12 (see treatment groups defined in [Table RHBH. 6.1.](#)).

Follow-up Population: Safety analyses for Period 4 (Post-Treatment Follow-up Period) will be conducted on the follow-up population, defined as all randomized patients who received at least 1 dose of study treatment and have entered the post-treatment follow-up period. Patients will be analyzed according to the treatment they actually received prior to entering Period 4.

[Table RHBH. 6.1.](#) describes the treatment groups and the comparisons for each study period and the analysis population.

Table RHBH. 6.1. Treatment Groups and Comparisons for Each Study Period and Analysis Population

Study Period	Analysis Population	Treatment Group	Abbreviation	Comparison
Induction Dosing Period (Period 2)	Intent-to-Treat Population; Per Protocol Set; Safety Population	Placebo	PBO	IXE80Q4W vs. PBO; IXE80Q2W vs. PBO; Overall ^a
		Ixekizumab 80 mg Q4W	IXE80Q4W	
		Ixekizumab 80 mg Q2W	IXE80Q2W	
		Total Ixekizumab	Total IXE	
		Total	Total	
Maintenance Dosing Period (Period 3)	Maintenance Dosing Period Primary Population (by Individual Dose)	Ixekizumab 80 mg Q4W/Placebo	IXE80Q4W/PBO	IXE80Q4W/IXE80Q4W vs IXE80Q4W/PBO; IXE80Q2W/IXE80Q4W vs IXE80Q2W/PBO Overall ^a
		Ixekizumab 80 mg Q4W/Ixekizumab 80 mg Q4W	IXE80Q4W/IXE80Q4W	
		Ixekizumab 80 mg Q2W/Placebo	IXE80Q2W/PBO	
		Ixekizumab 80 mg Q2W/ Ixekizumab 80 mg Q4W	IXE80Q2W/IXE80Q4W	
		Total	Total	
	Maintenance Dosing Period Primary Population (by Pooled Dose)	Ixekizumab/Placebo	IXE/PBO	IXE/IXE vs IXE/PBO
		Ixekizumab/Ixekizumab	IXE/IXE	
		Total	Total	
	Maintenance Dosing Period Secondary Population ^b	PlaceboResp/Placebo	PBOResp/PBO	No Comparison
		PlaceboNonR/Ixekizumab 80 mg Q4W	PBONonR/IXE80Q4W	

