convergence, the heterogeneous Toeplitz covariance structure, followed by the heterogeneous autoregressive covariance structure, followed by compound symmetry will be used. The Kenward-Roger method will be used to estimate the denominator degrees of freedom. Type III tests for the least-squares (LS) means will be used for the statistical comparison; the 95% CI will be reported. Treatment arm comparisons with placebo at Week 60 (Visit 19) and all other visits will be tested.

When the ANCOVA model is used, the model includes treatment and baseline value in the model. Type III sums of squares for the LS means will be used for the statistical comparison. For each treatment comparison performed, the LS mean for each treatment group, an estimate of the difference between treatments, corresponding 95% CI and p-value will be presented.

The time to relapse (loss of response; sPGA ≥ 3) during Period 3 is defined as:

$$\text{Time to relapse (days)} = \text{date of first sPGA} \geq 3 \text{ during Period 3} - \text{date of Week 12 re-randomization} + 1.$$

If a patient has not experienced relapse by completion or early discontinuation of Period 3, the patient will be censored at the date of their last visit during Period 3.

For each treatment group, a Kaplan-Meier plot of the time to relapse will be provided. The number of patients at risk and experiencing a relapse event by each scheduled visit during Period 3 will be presented by treatment group. Within each induction treatment group, maintenance treatment group comparisons will be performed using the log-rank test.

For the safety analyses, treatment group comparisons will be performed. Fisher's exact test will be used for all AE, baseline, discontinuation, and other categorical data. The continuous baseline characteristics will be analyzed using an ANOVA model with treatment as a factor. Continuous vital sign, and laboratory values will be analyzed by an ANCOVA model with treatment and baseline value as independent variables.

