6.4. Patient Disposition

Patient flow will be summarized from entered, to randomized, and to completion, and analysis populations will be listed and summarized by treatment group.

Patient disposition from study will be listed for the ITT population and summarized with reasons for disposition for the ITT population and the follow-up population, respectively. Patient disposition from study due to COVID-19 will also be listed.

Patient disposition from study treatment will be listed for the ITT population and summarized for the ITT population in Period 2 and the Maintenance Dosing Period Primary/Secondary/Relapse Population in Period 3 with reasons for disposition. Fisher's exact test will be used to test for a difference between and among treatment groups for the ITT population in Period 2 and the Maintenance Dosing Period Primary Population in Period 3. Patient disposition from study treatment due to COVID-19 will also be listed. The time to study treatment discontinuation due to any reason (in weeks) will be summarized by treatment group and graphically using Kaplan-Meier techniques, for each treatment period. The log-rank test will be used to compare time to study treatment discontinuation between treatment groups. The time to study treatment discontinuation will be calculated as:

$$\frac{\text{Date of study treatment discontinuation in period} - \text{Date of first dose in period} + 1}{7}$$

For Induction Dosing period, if the date of first dose is missing, the date of randomization will be used. Patients completing the study treatment will be censored at the date of completion (that is, the date of the last scheduled visit in the period). For the analyses of Period 3, if a patient

experiences relapse during the period, they will be censored at the date of relapse (Analysis populations: ITT Population, Maintenance Dosing Period Primary Population)

Patient allocation by center/site will be summarized with number of patients who entered the study, number of ITT patients for each treatment group, number of patients discontinued from study treatment, and number of patients discontinued from study.

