6.12.1.2. Period 3 (Maintenance Dosing Period)

6.12.1.2.1. Maintenance Dosing Period Primary Population and Maintenance Dosing Period Secondary Population

The duration of exposure on maintenance treatment will be calculated as:

$$\begin{aligned} & \textit{Duration of maintenance exposure (days)} \\ &= \textit{Date of last visit (scheduled or unscheduled) or relapse in Period 3} \\ & \quad - \textit{Date of first dose in Period 3} + 1 \end{aligned}$$

Note that patients who experience a relapse during Period 3 will only have their maintenance exposure calculated up until the date of relapse.

The number and percentage of patients in each of the following categories will be summarized: >0 days, ≥7 days, ≥14 days, ≥30 days, ≥60 days, ≥90 days, ≥120 days, ≥183 days, and ≥365 days. Note that patients may be included in more than one category. The number and percentage of patients falling into the following subcategories will also be summarized: >0 to <7 days, ≥7 to <14 days, ≥14 to <30 days, ≥30 to <60 days, ≥60 to <90 days, ≥90 to <120 days, ≥120 to <183 days, ≥183 to <365 days, and ≥365 days.

The summaries will also include the following information:

- Total exposure in patient years, calculated as:

$$\begin{aligned} & \textit{Maintenance exposure in patient years} \\ &= \frac{\textit{Sum of duration of maintenance exposure for all patients in treatment group}}{365.25} \end{aligned}$$

- Mean and median total dose (in mg). For those patients randomized to 80 mg Q4W, the total dose (in mg) taken during Period 3 will be calculated as follows:

$$\begin{aligned} & \textit{Total Period 3 dose} \\ &= \textit{Total number of active injections (including loading doses) received in} \\ & \quad \textit{Period 3 prior to relapse} \times 80 \end{aligned}$$

Note that the total number of injections received will be calculated using the response to the question ‘Was dose administered?’ on the *Exposure as Collected* eCRF page and the actual dose description from IWRS study drug dispense dataset.

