Adverse events and TEAEs will be summarized for the following time periods and analysis populations:

- Period 2 (Safety Population)
- Period 3 (Maintenance Dosing Period Primary/Secondary/Relapse Population)
- Period 4 (Follow-up Population)

An overall summary of AEs including the number and percentage of patients who experienced TEAE, TEAE by maximum severity, death, SAE, TEAE possibly related to study treatment, discontinuations from the treatment due to an AE, and TEAEs of special interest will be performed for Periods 2 (Safety Population) and 3 (Maintenance Dosing Period Primary/Secondary/Relapse Population).

The following summaries/analyses will be performed for Periods 2 (Safety Population) and 3 (Maintenance Dosing Period Primary Population), unless noted otherwise:

- TEAE by SOC and PT.
- TEAE by PT.
- TEAE by maximum severity, SOC, and PT.

Follow-up emergent AEs will be summarized for the Follow-Up Population in Period 4:

- FEAE by PT.

In general, for all AE-related summaries, the number and percentage of patients experiencing the events will be presented by treatment group. In general, events will be ordered by decreasing frequency in the total ixekizumab group, followed in the order of ixekizumab Q2W, ixekizumab Q4W, and placebo (when applicable) group, within SOC and/or PT for sorting. For events that are gender-specific (as defined by MedDRA), the denominator and computation of the percentage will include only patients from the given gender.

A by-patient listing of all AEs for safety population will be provided.

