6.12.4. Clinical Laboratory Evaluation

Clinical laboratory assessments include hematology, serum chemistry, urinalysis, and safety-related immune markers such as neutrophil counts. All laboratory tests will be presented using the international system of unit (SI).

Continuous laboratory tests will be summarized as changes from baseline to last observation for patients who have both baseline and at least 1 postbaseline result for Periods 2 and 3:

- The scheduled visits/measurements will be included. The unscheduled visits and the repeat measurements will be excluded.
- For Safety Population during Period 2 and Maintenance Dosing Period Primary Population during Period 3, treatment group comparisons will be conducted using an ANCOVA model with treatment group and baseline value in the model.
- Data will be analyzed based on original scale.

Laboratory test observed values at each visit (starting at baseline) and change from baseline to each scheduled visit, respectively, will be displayed in box plots for patients who have both a baseline and at least one postbaseline result for Periods 2 and 3. These box plots will be used to evaluate trends over time and to assess a potential impact of outliers on central tendency summaries.

- The scheduled visits/measurements will be included. The unscheduled visits and the repeat measurements will be excluded.
- The following summary statistics will be included as a table below the box plot: number of patients with a baseline and at least one postbaseline result, mean, standard deviation, minimum, Q1, median, Q3, and maximum.
- Data will be summarized based on original scale.
- On the box plots of the laboratory test observed values, the lines of the reference ranges/limits (by using the performing laboratory reference ranges) will be added. In cases where limits vary across age and gender, the lowest of the high limits and the highest of the low limits will be used.

The number and percentage of patients with a treatment-emergent or follow-up emergent abnormal, high, or low for laboratory tests will be summarized by treatment group for each study period. The comparisons between and among treatment groups will be conducted using Fisher's exact test for the Safety Population for Period 2 and Maintenance Dosing Period Primary Population for Period 3.

- All scheduled, unscheduled and repeated measurements will be included.

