6.13.2.3. Analyses of ADA Effects on Specific Adverse Events

The analyses of ADA effects on safety will be conducted on all evaluable patients within the defined safety population for Period 2 and Combined Induction and Maintenance Dosing Periods (Combined Periods 2 and 3, information prior to relapse).

Baseline definition for immunogenicity analyses for the Combined Treatment Period is the same as [Table RHBH. 6.10](#).

AESIs of allergic reaction/hypersensitivity (anaphylaxis and non-anaphylaxis) and of injection site reactions will be included in an assessment of AE to TE-ADA over time. Timing of an AE will be taken to be the reported AE start date.

For each TE-ADA status dichotomous variable (as defined in [Table RHBH. 6.11](#).), patients will be categorized according to whether they were (i) always in lesser-TE-ADA status post-baseline or (ii) at some point post-baseline were in greater-TE-ADA status. For each AESI, within the time-varying TE-ADA status groups, a summary will be provided of the number of patients who had no event, events only while in lesser-TE-ADA status for group (i), or – for group (ii) – at least 1 event while in greater-TE-ADA status.

Additionally, summaries will be provided of the total number of AESI events (with unique start dates) by time-varying TE-ADA status groups at the event date. The summaries will aggregate time respectively, in greater-TE-ADA status and in lesser-TE-ADA status, along with the event rates (rates per 100 patient-years) relative to those aggregate times.

By-patient listings will be provided of patients with TE-ADA who experience a treatment-emergent allergic reaction/hypersensitivity reaction or an injection site reaction.

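### Period 3 adverse events are compared as crude percentages by Fisher's exact test although follow-up stops at relapse, so the shorter placebo follow-up makes common events look more frequent on ixekizumab

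*SAP*

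**What the plan says.** SAP 6.1.1 defines the Maintenance Dosing Period Primary Population and adds: "Only information prior to relapse will be presented". The exposure section (SAP 6.12.1.2.1) follows suit: "patients who experience a relapse during Period 3 will only have their maintenance exposure calculated up until the date of relapse". Protocol 12.2.1.2 states the cut at relapse only for the maintenance-of-effect analyses. It is the SAP that applies it to the whole population, safety included.

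For adverse event tables, SAP 6.12.2 says that "the number and percentage of patients experiencing the events will be presented by treatment group". The Period 3 test is fixed in SAP 6.1.3.1, and in the same words in Protocol 12.2.1.2: Fisher's "exact test will be used for all AE, baseline, discontinuation, and other categorical data". SAP Table RHBH.6.8 repeats it for most special safety topics. SAP 6.12.4 uses Fisher's "exact test for the Safety Population for Period 2 and Maintenance Dosing Period Primary Population for Period 3" for treatment-emergent laboratory abnormalities. SAP Table RHBH.6.1 sets the contrasts: within each induction regimen, and pooled as "IXE/IXE vs IXE/PBO".

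No between-arm analysis of Period 3 adverse events allows for length of follow-up. The only person-time analysis of adverse events is in SAP 6.13.2.3, which gives "event rates (rates per 100 patient-years) relative to those aggregate times". It covers allergic and injection-site events by antibody status, not by treatment arm.

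The SAP does allow for follow-up elsewhere in this population. For time to treatment discontinuation (SAP 6.4), if a patient "experiences relapse during the period, they will be censored at the date of relapse", and the arms are compared by Kaplan-Meier and log-rank. Protocol 9.4.2 also reports earlier maintenance-period adverse events as exposure-adjusted rates.

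**The concern.** Follow-up ends at an event that treatment is meant to prevent. SAP 5.3 plans on 70% against 10% maintaining sPGA (0,1) to Week 60, and Protocol 9.4.2 cites 71% against 7% from earlier studies. Losing sPGA (0,1) is not the same as relapse (sPGA 3 or more), but the direction is clear: placebo patients leave observation sooner.

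A patient watched for 20 weeks has less opportunity to report an event than one watched for 40. For any event with a continuing hazard, the placebo percentage falls even if the two hazards are identical, and Fisher's test treats that shortfall as a treatment difference. Most exposed are the any-TEAE row and the most frequent terms. A small p-value there could be read as a long-term safety signal, or a true advantage of ixekizumab could be masked.

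**Working it through.** **The plan's own figures.** SAP 5.3: 0.70 × 168 = 117.6, split 2:1 into 78.4 and 39.2, which matches 78 and 39 per induction regimen. Pooled, this is 156 and 78. Enumerating Fisher's test for 70% against 10% at two-sided 0.025 gives power above 99.99%, in line with the stated >99%.

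**Inputs from the documents.** Follow-up runs from Week 12 to Week 60, so 48 weeks. Relapse is assessed at each visit (Protocol 7.1.3), at least every 4 weeks (Table RHBH.9.2). Planned completers are 336 of 420 = 80% (Protocol synopsis).

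**Assumptions, because the documents give no value.**
- Relapse over 48 weeks (placebo/ixekizumab): 90%/30%, 75%/20% or 60%/15%.
- Relapse-free lag: 0 or 8 weeks.
- The 20% dropout spreads evenly over 60 weeks in both arms.
- The safety test is two-sided at 0.05.
- The adverse event hazard is the same in both arms.

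**Formulas.**
- Relapse hazard l = −ln(1 − relapse)/(48 − lag). For 90% with no lag, 2.303/48 = 0.0480 per week; for 30%, 0.357/48 = 0.0074.
- Dropout hazard d = −ln(0.8)/60 = 0.0037 per week.
- At-risk curve S(t) = exp(−l·max(0, v − lag))·exp(−d·t), where v is the last 4-weekly visit at or before t.
- Mean follow-up = ∫S(t)dt over 48 weeks.
- Crude incidence = ∫h·exp(−ht)·S(t)dt.
- Fisher rejection: exact enumeration of both binomials.

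**Results at the two ends of the range, constant and equal hazards.**

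| | 90%/30%, no lag | 60%/15%, lag 8 weeks |
|---|---|---|
| Mean follow-up, placebo vs ixekizumab (weeks) | 19.5 vs 37.7 | 32.9 vs 41.5 |
| Follow-up ratio | 0.52 | 0.79 |
| Crude incidence at 1 per year, placebo vs ixekizumab | 28.7% vs 49.2% | 44.6% vs 53.4% |
| Fisher rejection at 1 per year, pooled; one stratum | 85%; 56% | 21%; 13% |
| At 0.3 per year | 39%; 18% | 9.5%; 5.8% |
| At 0.1 per year | 11%; 2.5% | 4.5%; 2.3% |
| At 0.05 per year | 2.9%; 0.4% | 2.6%; 1.2% |

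At 0.3 per year and above, over 90% of these rejections show ixekizumab as worse.

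**Front-loaded hazards.** With cumulative hazard 0.3 over 48 weeks and a half-life of 4 to 16 weeks, Fisher's test rejects in 4% to 22% pooled and 4% to 11% in one stratum. Under the same hazards the exposure-adjusted rate ratio (ixekizumab/placebo) is 0.60 to 0.90 with no true difference, so dividing by patient-years errs in the other direction.

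**Log-rank censored at relapse.** In 1000 simulated null trials per setting, at the two end scenarios, with constant and front-loaded hazards and both sample sizes, it rejects in 3.7% to 6.7% (Monte Carlo standard error about 0.7 points). If adverse event risk and relapse share a patient-level gamma frailty of variance 0.5 or 1, it rejects in 2.2% to 13.9%. In the worst pooled case (90%/30%, no lag, 1 event per year) that is 6.7% to 13.9% with frailty, against 63.7% to 74.8% for Fisher's test.

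**The case against.** The strongest reply is that this matters little and is shown only by assumption. Period 2 is the primary safety comparison (Protocol 12.2.8). Period 3 safety p-values lie outside the gatekeeping (SAP 6.3). Patient-years and time to relapse are tabulated by arm, so a reader can see the imbalance. The tilt makes ixekizumab look worse and cannot hide harm. All of that stands and limits the importance of the point, but a separate exposure table does not correct a p-value.

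It also stands that 90% relapse on placebo is an upper limit. Failure to maintain sPGA (0,1) includes sPGA 2 and missing data, and the 85% figure needs that limit together with no lag, a constant hazard of 1 per year and pooling. Yet the mildest constant-hazard scenario still gives 21% pooled for a common event.

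A further objection is that the remedy reaches past the problem: Fisher's test is not inflated for rare terms, yet serious and special-interest events would also get the new analysis. This is partly fair. The crude percentages do remain tilted for rare events (about 0.7% placebo against 1.4% ixekizumab at 0.02 per year in the 90%/30% case) even when the test does not reject, and counts can be shown where a hazard ratio cannot be estimated.

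Finally, the program safety analysis plan may supersede the SAP on special topics (SAP 6.12.3.1). It is not among the documents. That provision does not extend to the general adverse event tables.

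**Conclusion.** The concern holds. In the Period 3 Primary Population, unequal follow-up caused by treatment enters the adverse event and laboratory comparisons uncorrected. Under the assumed relapse range and equal constant hazards, false rejection for an event at 1 per patient-year is 21% to 85% pooled and 13% to 56% in one stratum. It fades to nominal or below for events at 0.05 per year, and in a single stratum already at 0.1 per year. The size rests on assumed relapse rates, event hazards and test level. The direction rests on the documents, for events whose hazard continues. No primary or major secondary conclusion is affected. It should be fixed because the comparison is the only randomised safety evidence after Week 12 and the remedy is cheap.

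**What to change.** In SAP 6.1.3.1 and 6.12.2, add a time-to-first-event analysis censored at relapse, with Kaplan-Meier curves, log-rank test and hazard ratio with confidence interval. Apply it to any TEAE, common TEAEs, serious events and the special-interest categories, and read Period 3 between-arm differences from it. Where an arm has no event, show counts only. State that censoring at relapse is assumed non-informative.

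Keep the protocol-stated counts, percentages and Fisher's test, including for laboratory abnormalities, and label them as not adjusted for unequal follow-up. Rates per 100 patient-years may be added as description, with a note that front-loaded events make them favour the arm followed longer. They should not carry the inference.

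The cost is modest programming: the relapse date and the censoring rule already exist in SAP 6.1.3.1 and 6.4, and no protocol-stated table is dropped. The remaining weakness is informative censoring, which in the frailty simulations took the log-rank error to at most 13.9%.
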